## 2. ALGORITHM FOR PRIOR / CONCOMITANT /POST-TREATMENT MEDICATIONS AND PROCEDURES:

Start Date	End Date	Action
Known	Known	
If medication/procedure end date < first drug administration start date, assign as prior
 
If medication/procedure start date < first administration of full treatment period study drug (2nd 800 µg dose) and medication/procedure start or end date >= first drug administration, assign as titration period (Concomitant)
 
If medication/procedure start date <= 28 days after last administration of study drug date and medication/procedure start or end date > first administration of full treatment period study drug (2nd 800 µg dose, assign as full treatment period (Concomitant)
 
If medication/procedure start date > 28 days after last administration of study drug date, assign as post-treatment

	Partial	
Impute medication/procedure end date as latest possible date (i.e. last day of month if day unknown or 31st December if day and month are unknown), then:
 
If medication/procedure end date < first study drug administration start date, assign as prior
 
If medication/procedure start date < first administration of full treatment period study drug (2nd 800 µg dose) and medication/procedure start or end date >= first study drug administration, assign as titration period (Concomitant)
 
If medication/procedure start date <= 28 days after last administration of study drug date and medication/procedure start or end date > first administration of full treatment period study drug (2nd 800 µg dose, assign as full treatment period (Concomitant)
 
If medication/procedure start date > 28 days after last administration of study drug date (section 7.7.4), assign as post-treatment

Start Date	End Date	Action
Known	Missing/ Ongoing	
If medication/procedure end date is missing/ongoing could never be assumed a prior medication
 
Assign as titration period and full treatment period (Concomitant) unless, if medication/procedure start date <math>\geq</math> first administration of full treatment period study drug (2nd 800 µg dose), assign as full treatment period (Concomitant)
 
If medication/procedure start date <math>></math> 28 days after last administration of study drug date (section 7.7.4), assign as post-treatment

Partial	Known	
Impute medication/procedure start date as earliest possible date (i.e. first day of month if day unknown or 1st January if day and month are unknown), then:
 
If medication/procedure end date <math><</math> first study drug administration start date, assign as prior
 
If medication/procedure start date <math><</math> first administration of full treatment period study drug (2nd 800 µg dose) and medication/procedure start or end date <math>\geq</math> first drug administration, assign as titration period (Concomitant)
 
If medication/procedure start date <math>\leq</math> 28 days after last administration of study drug date and medication/procedure start or end date <math>></math> first administration of full treatment period study drug (2nd 800 µg dose, assign as full treatment period (Concomitant).
 
If medication/procedure end date <math>\geq</math> first drug administration start date and medication/procedure start date <math>></math> 28 days after last administration of study drug date (section 7.7.4), assign as post-treatment

Start Date	End Date	Action
Partial	Partial	
Impute medication/procedure start date as earliest possible date (i.e. first day of month if day unknown or 1st January if day and month are unknown) and impute medication/procedure end date as latest possible date (i.e. last day of month if day unknown or 31st December if day and month are unknown), then:
 
If medication/procedure end date < first drug administration start date, assign as prior
 
If medication/procedure start date < first administration of full treatment period study drug (2nd 800 µg dose) and medication/procedure start or end date >= first study drug administration, assign as titration period (Concomitant)
 
If medication/procedure start date <= 28 days after last administration of study drug date and medication/procedure start or end date > first administration of full treatment period study drug (2nd 800 µg dose, assign as full treatment period. (Concomitant)
 
If medication/procedure end date >= first study drug administration start date and medication/procedure start date > 28 days after last administration of study drug date (section 7.7.4), assign as post-treatment

	Missing/ongoing	
Impute medication/procedure start date as earliest possible date (i.e. first day of month if day unknown or 1st January if day and month are unknown), then :
 
If medication/procedure end date is missing could never be assumed a prior medication
 
Assign as titration period and full treatment period (Concomitant) unless, if medication/procedure start date >= first administration of full treatment period study drug (2nd 800 µg dose), assign as full treatment period (Concomitant)
 
If medication/procedure start date > 28 days after last administration of study drug date (section 7.7.4), assign as post-treatment

Missing	Known	
If medication/procedure end date < first study drug administration start date, assign as prior
 
If medication/procedure end date < full treatment period study drug (2nd 800 µg dose, assign as titration period (Concomitant)
 
Else assign as titration period and full treatment period (Concomitant).
 
Cannot be assigned as post-treatment

Start Date	End Date	Action
Missing	Partial	
Impute medication/procedure end date as latest possible date (i.e. last day of month if day unknown or 31st December if day and month are unknown), then:
 
If medication/procedure end date < first study drug administration start date, assign as prior
 
If medication/procedure end date < full treatment period study drug (2nd 800 µg dose, assign as titration period (Concomitant)
 
Else assign as titration period and full treatment period (Concomitant).
 
Cannot be assigned as post-treatment

	Missing/ongoing	Assign as titration period and full treatment period. (Concomitant)

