### **6.7.5. TREATMENT PERIOD**

Treatment period start for medications, procedures and AEs is defined as:

- First administration of study drug.

Titration period start for AEs, medications and procedures is defined as:

- First administration of study drug.

Full treatment period start for AEs, medications and procedures is defined as:

- First administration of full treatment period study drug (i.e., second dose of 800 µg).

Treatment period end for medications, procedures and AEs is defined as:

- Last administration of study drug date plus 28 days.
- For AEs onset dates/times are recorded, so the calculation of period starts/ends will take account of both dates and times.

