## 12. MEDICATIONS AND PROCEDURES

Medications taken prior to and during the conduct of the study will be obtained from the Concomitant Medications eCRF and will be coded using World Health Organization Drug Dictionary (WHO-DD) Enhanced Version 01MAR2016E/WHO Herbal Dictionary.

Procedures performed during the conduct of the study will be obtained from the Concomitant Procedures eCRF and coded using the MedDRA coding dictionary, version 19.1.

Medications are allocated to a study period as follows:

- Prior medication: Any medication that started and stopped prior to first administration of study drug.
- Concomitant medications taken during the treatment period: Any medication that started or stopped on or after first administration of study drug up to and including 28 days after last administration of study drug, or is ongoing. Concomitant medications will be presented for titration period and full treatment period.
  - Titration period: Any medication that started or stopped on or after first administration of study drug up to first administration of full treatment period study drug, or is ongoing.
  - Full treatment period: Any medication that started or stopped on or after first administration of full treatment period study drug (i.e. 2nd 800 µg dose) up to and including 28 days after last administration of study drug, or is ongoing.
- Post-treatment medications: Any medication that started more than 28 days after last administration of study drug.

Procedures are allocated to a study period as follows

---

Document: ATX\_GD\_59 Final 1.0 SAP 28FEB2018.docx  
Author: [name]

Version Number: Final 1.0  
Version Date: 28FEB2018

Template No: CS\_TP\_BS016 Revision 4  
Effective Date: 01Apr2016

Reference: CS\_WI\_BS005

Copyright © 2009, 2010, 2012, 2016 Quintiles Transnational Corp. All rights reserved.  
The contents of this document are confidential and proprietary to Quintiles Transnational Corp. Unauthorized use, disclosure or reproduction is strictly prohibited.

- o Concomitant procedures taken during the treatment period: Any procedure that started or stopped on or after first administration of study drug, up to and including 28 days after last administration of study drug, or is ongoing. Procedures will be similarly broken down by titration and full treatment period as for medications.
- o Post-treatment procedures: Any procedure that started more than 28 days after last administration of study drug.

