Study periods for medications and procedures are mutually exclusive, therefore a medication or procedure can be only be assigned to one period, namely Prior, Concomitant or Post-treatment. Within concomitant medications and procedures the titration period and full treatment period are not mutually exclusive; hence a medication or procedure can be assigned to the titration period, full treatment period or both. Any medication ongoing during a treatment period will be included even if it started in an earlier period but has not ended before the start of the next period.

Note that the denominator for percentages of subjects is the total number of subjects in the ITT population with data available for the respective period. The denominator for percentages of events is the total number of events in the respective period.

See Appendix 2: Partial Date Conventions for handling of partial dates for medications/ procedures. In the case where it is not possible to define a medication/ procedure as prior, concomitant (titration period/full treatment period for medications), or post-treatment, the medication/ procedure will be classified by the worst case; i.e. titration period (concomitant) if it cannot be ruled out by the partial or missing date(s) recorded.

The following tables will be presented for the ITT population:

- The number (n) and percentage (%) of subjects with at least one medication and frequency of medications: Prior medication, concomitant medication taken during the treatment period, broken down by titration period and full treatment period, and overall and post-treatment medication taken more than 28 days after the last administration of study drug, will be presented overall and by Anatomic Therapeutic Class (ATC) Level 1 and within ATC Level 1 by ATC Level 3 and within ATC Level 3 and by WHO-DD Preferred Drug name. If medication occurred more than once for a subject within a period, the subject will only be counted once per ATC Level/Preferred drug name in that period.
- The number (n) and percentage (%) of subjects with at least one prior, concomitant (concomitant procedures occurring during the treatment period, broken down by titration period and full treatment period, and overall) and post-treatment procedures will be presented overall and by MedDRA SOC and within SOC by PT. If a procedure occurred more than once for a subject within a period, the subject will only be counted once per MedDRA SOC or PT in that period.

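### SAP Appendix 2 leaves the day of the second 800 µg dose out of the full treatment period for medications and procedures, contrary to section 12; both texts can also assign that period to subjects who never reached it

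*SAP*

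**What the plan says.** SAP section 6.7.5 starts the full treatment period, for medications and procedures as well as adverse events, at the second 800 µg dose. Section 12 matches this and includes the boundary day: "Full treatment period: Any medication that started or stopped on or after first administration of full treatment period study drug". Procedures are split in the same way.

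Appendix 2, part 2, turns these definitions into rules by type of start and end date. The rows known/known, known/partial, partial/known and partial/partial (start/end) share these conditions:

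- Prior, as worded in the known/known row: "If medication/procedure end date < first drug administration start date, assign as prior".
- Titration: "If medication/procedure start date < first administration of full treatment period study drug", with a start or end on or after the first dose.
- Full treatment: start no later than 28 days after the last dose, and "medication/procedure start or end date > first administration of full treatment period study drug".
- Post-treatment: start more than 28 days after the last dose.

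The known/ongoing and partial/ongoing rows read "Assign as titration period and full treatment period (Concomitant) unless" the start is on or after the second 800 µg dose, in which case only full treatment is assigned. At this same boundary, these rows use `>=`. The rows with a missing start date default to both periods unless an end date shows otherwise.

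Section 12 also counts any ongoing medication in the full treatment period. Its percentage denominator is the "total number of subjects in the ITT population with data available for the respective period".

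**The concern.** The titration rule needs a start strictly before the boundary date, and the full treatment rule needs a start or end strictly after it. The boundary day itself is therefore in neither. It is a dosing day for every continuing subject, and same-day start and stop is ordinary for a procedure or a single dose of a symptomatic treatment.

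The ongoing rule raises a different question. A subject who leaves during titration has no second 800 µg dose and so no full treatment period, yet an ongoing medication is assigned to that period by default. The numerator could then include subjects whom the denominator leaves out.

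At stake is the accuracy of the concomitant medication and procedure tables by period, and of the period flags in the listings.

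**Working it through.** The plan gives no figure to reproduce. The check applies the known/known rules as written and compares the result with section 12.

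Inputs: first dose Day 1 (section 6.1); second 800 µg dose at Week 10, nominal Day 70, and last dose at Week 18, nominal Day 126 (visit window table, Appendix 4 section 4.2). The end of treatment is then Day 126 + 28 = Day 154. Comparison is by date, because sections 6.7.5 and 6.7.6 bring in clock times for adverse events only.

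| Start–end | Prior: end < 1 | Titration: start < 70 and (start or end ≥ 1) | Full: start ≤ 154 and (start or end > 70) | Post: start > 154 | Appendix 2 | Section 12 |
|---|---|---|---|---|---|---|
| 70–70 | no | no | no | no | none | full |
| 69–70 | no | yes | no | no | titration | titration and full |
| 71–71 | no | no | yes | no | full | full |

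All pairs with −40 ≤ start ≤ end ≤ 217 were then tested. That is 258 grid days, so 258 × 259 / 2 = 33,411 pairs. (The grid includes a Day 0 that section 6.1 skips; this does not alter the pattern.)

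- Unassigned under Appendix 2: 1 pair (70–70).
- Titration only, where section 12 gives both: 110 pairs (starts −40 to 69, end 70).
- Total disagreements: 1 + 110 = 111, all with an end date on the dosing day.
- With `>=` in the full treatment rule: 0 unassigned, 0 disagreements.

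These count possible date combinations, not expected records.

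The partial-date rows differ in how they fail. No period at all requires start and end both to equal the dosing day. In known/partial the end is imputed to the last day of a month or year, so the dose must fall on that day. In partial/known the start is imputed to the first day, so the dose must fall there. In partial/partial the two imputed dates cannot coincide. The titration-only error is less restricted: in partial/known it occurs whenever the known end is the dosing day and the imputed start is earlier.

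For ongoing medications, take a subject last dosed at Week 4 (Day 28) with a drug started on Day 10 and still ongoing. The known/ongoing row gives titration and full treatment, because its only exception refers to a dose this subject never received. Section 12 has the same open clause. In the missing/known and missing/partial rows, the final catch-all also gives both periods; missing/missing gives both outright.

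For size, the protocol synopsis expects about 15 subjects dosed and about 12 completing. It does not say when the others stop. Assume 0 to 3 stop before Week 10, each on an ongoing drug: the full-treatment numerator then includes 0 to 3 subjects who never entered the period.

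**The case against.** **Appendix 2 is for partial dates.** Its title concerns partial dates and times, and the main text refers to it for that purpose, so section 12 could be taken to govern complete dates. Nothing states which text prevails, however, and the appendix has an explicit known/known row. A programmer has two conflicting rules. Nor is the strict inequality evidently deliberate, since the ongoing rows use `>=` at the same date.

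**Other safeguards.** Section 12's worst-case fallback and the data review check in Appendix 4 section 4.4 address partial or missing dates. They may catch errors in those rows, but not a complete-date record.

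**Stronger readings.** A reader might infer that the gap weakens the safety review between the second and third 800 µg doses, or the Data Monitoring Committee's review. The documents do not support this. The algorithm serves the final analysis; section 5.1 has Data Management supply the Committee's listings, with no Biostatistics analysis; and the protocol's list of Committee outputs does not name concomitant medications. Nor are medication counts among the safety endpoints in section 3.1. The records are not lost either: section 12 lists medications and procedures by subject, where a blank period would show, and injection reactions are captured as adverse events and in the diary.

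**Ongoing medications.** This is not a departure of the appendix from section 12, because both have the gap. It can be argued that a subject without the second 800 µg dose has no full treatment period, and that the denominator wording excludes that subject. That is probably the intent, but it does not correct the numerator rule. A large percentage distortion is tempting to calculate, but it would need invented withdrawal times and drug use, and a choice of denominator that the text leaves open.

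**Conclusion.** Wrong as written, and minor. Four Appendix 2 rows contradict section 12 at the day of the second 800 µg dose. With complete dates, a record confined to that day receives no period. Because Appendix 2 reaches concomitant status only through titration or full treatment, the record also leaves the concomitant counts. One that started earlier and stopped that day loses its full treatment assignment.

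The ongoing and missing-start rules, in section 12 as well as Appendix 2, lack a condition that the full treatment period was entered. The SAP applies that limit elsewhere: section 13 keeps early withdrawals out of later dose levels, and section 15.1 bases adverse event percentages on subjects dosed in the period.

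The result rests on a literal reading and date-only comparison. The number of affected records cannot be derived from the documents; the 0 to 3 excess subjects are an illustration under the stated assumption. Adverse event and efficacy analyses, interim reviews and the listed safety endpoints are unaffected.

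**What to change.** 1. In the known/known, known/partial, partial/known and partial/partial rows of Appendix 2, part 2, change `>` to `>=` in the comparison with the second 800 µg dose. The rows then agree with section 12, and no rule of precedence between the two texts is needed.
2. In section 12, and in the five Appendix 2 rows with a missing or ongoing end date or a missing start date, state that the full treatment period is assigned only if the subject received the second 800 µg dose. State that the denominator for that period is restricted in the same way. Editing Appendix 2 alone would leave the section 12 clause open.

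The cost is one operator in four rows and one condition in section 12 and five rows, with matching program changes. No new data are needed.

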## APPENDIX 3. CONVERSION FACTORS TO SYSTÈME INTERNATIONAL UNITS

System	Panel	Parameter	Reported Unit	Conversion Factor	SI Unit
Haematology	Erythrocytes and Platelets	RBC Count	10  /uL	1.0	10  /L
		Haemoglobin	g/dL	10.0	g/L
		Haematocrit	%	0.01	V/V
		MCV	fL	1.0	fL
		MCHC	g/dL	1.0	g/dL
		Platelet count	10  /uL	1.0	10  /L
	Leukocytes	WBC Count	10  /uL	1.0	10  /L
		Neutrophils	10  /uL	1.0	10  /L
		Neutrophils (%)	%	1.0	%
		Lymphocytes	10  /uL	1.0	10  /L
		Lymphocytes (%)	%	1.0	%
		Monocytes	10  /uL	1.0	10  /L
		Monocytes (%)	%	1.0	%
		Eosinophils	10  /uL	1.0	10  /L
		Eosinophils (%)	%	1.0	%
		Basophils	10  /uL	1.0	10  /L
		Basophils (%)	%	1.0	%

System	Panel	Parameter	Reported Unit	Conversion Factor	SI Unit
Biochemistry	Liver Function	Total Bilirubin	mg/dL	17.1	umol/L
		AST	U/L	1.0	U/L
		ALT	U/L	1.0	U/L
		ALP	U/L	1.0	IU/L
	Electrolytes/ Minerals	Sodium	mEq/L	1.0	mmol/L
		Potassium	mEq/L	1.0	mmol/L
		Chloride	mEq/L	1.0	mmol/L
		Bicarbonate	mEq/L	1.0	mmol/L
		Calcium	mg/dL	0.25	mmol/L
		Phosphate	mg/dL	0.323	mmol/L
	Lipids/ Proteins	Serum Proteins	g/dL	10.0	g/L
	Other Chemistry	Urea	mg/dL	0.357	mmol/L
		Creatinine	mg/dL	88.4	umol/L
		Uric Acid	mg/dL	59.48	umol/L
Urinalysis		pH	(none)	1.0	(none)
		Specific Gravity	(none)	1.0	(none)
Thyroid Panel		FT3	pg/mL	1.54	pmol/L
		FT4	ng/dL	12.92	pmol/L
		TSH	uIU/mL	1.0	mIU/L

RBC = Red Blood Cell. WBC = White Blood Cell. MCV = Mean Corpuscular Volume. MCHC = Mean Corpuscular Haemoglobin Concentration. AST = Aspartate Aminotransferase. ALT = Alanine Aminotransferase. ALP = Alkaline Phosphatase. FT3 = Free Triiodothyronine. FT4 = Free Thyroxine. TSH = Thyroid Stimulating Hormone. SI = Système International.

Document: ATX\_GD\_59 Final 1.0 SAP 28FEB2018.docx  
 Author: [name]

Version Number: Final 1.0  
 Version Date: 28FEB2018

Template No: CS\_TP\_BS016 Revision 4  
 Effective Date: 01Apr2016

Reference: CS\_WI\_BS005

Copyright © 2009, 2010, 2012, 2016 Quintiles Transnational Corp. All rights reserved.  
 The contents of this document are confidential and proprietary to Quintiles Transnational Corp. Unauthorized use, disclosure or reproduction is strictly prohibited.

## APPENDIX 4. POPULATION ASSIGNMENT AND DATA REVIEW PLAN

### 1. INTRODUCTION

Prior to the final locking of the clinical study database of the ATX-GD-59-001 study, a DR is to be performed in order to meet the following objectives:

- Establish and finalise the analysis populations.
- Identify major protocol deviations programmatically and by means of the 'Protocol Deviations' log recorded in the IQVIA Clinical Trial Management System (CTMS).
- Discuss any data issues or outliers, not resolved and indicated as such in the data handling report (DHR), which might affect the analysis or require revision to the SAP.
- Evaluate visit deviations in terms of the protocol visit windowing, including mapping of ET visits to a scheduled visit, if applicable.

A clean snapshot of the clinical study database is to be considered as the source for the production of the DR meeting deliverables. The IQVIA BIOS and IQVIA Data Management DR deliverables will be produced based on the same clean snapshot provided by Data Management.

### 2. DELIVERABLES FROM IQVIA DATA MANAGEMENT

The final analysis will be performed following a pre-database lock DR meeting to determine population assignment and on a clean snapshot of the clinical study database with all data management procedures completed, including:

The following procedures need to be completed by IQVIA Data management:

- All outstanding data issues and queries resolved.
- All unresolved data issues that will remain present in the clinical study database are to be documented in the DHR, and provided to the IQVIA Statistical Team Lead (STL) and DR meeting attendees. This is a report containing a list of queries from both eCRF- and non-eCRF data that could not be resolved by sites following identification using edit checks/manual data reviews and are to remain present in the clinical study database at the DR.
- All coding of medications, procedures, medical history and AEs completed and authorised.

Document: ATX\_GD\_59 Final 1.0 SAP 28FEB2018.docx  
Author: [name]

Version Number: Final 1.0  
Version Date: 28FEB2018

Template No: CS\_TP\_BS016 Revision 4  
Effective Date: 01Apr2016

Reference: CS\_WI\_BS005

Copyright © 2009, 2010, 2012, 2016 Quintiles Transnational Corp. All rights reserved.  
The contents of this document are confidential and proprietary to Quintiles Transnational Corp. Unauthorized use, disclosure or reproduction is strictly prohibited.

- SAEs reconciliation with the Safety Database completed.
- All reconciliation of external vendor data with the eCRF data completed successfully.
- The data review listings of all the data in the clean snapshot of pre-database lock datasets have been reviewed and no further data anomalies other than unresolvable data anomalies are present.

